4.1 Screening/Enrollment period

Prior to inclusion into the study, patients will undergo screening. All patients must sign the Informed Consent Form and if applicable, any locally required privacy act document authorization must also be obtained prior to the start of any screening procedures. All screening procedures must be performed within 28 days before dosing (Day -28 to Day -1).

Consenting patients are assessed (Table 5) to ensure that they meet eligibility criteria and to discontinue other therapies, if required (Section 3.1, Section 3.4). Patients who do not meet these criteria must not be entered into the study.

All patients agree to provide a sample of their archival FFPE tumor sample (or approximately 20 unstained sections mounted on glass slides prepared from the block) from the primary or recurrent cancer for entry into this study, and a blood sample which may be used for a subsequent confirmatory *BRCA* mutation test using the Myriad BRACAnalysis CDx[®] test. If archival tumor sample is not available tumor sample from fresh biopsy is acceptable.

4.2 Treatment period

Descriptions of the procedures for this period are included in the Schedule of Assessments (Table 5) with exceptions of the following specific requirements for the treatment period:

The Study conduct period starts at the time of administration of the first dose of IPs (cediranib plus olaparib). There is no maximum duration for taking IPs in this study.

While on study treatment, patients will be required to attend study visits every week during the first 4 weeks, every 2 weeks during the next 4 weeks and every 4 weeks (± 3 days) thereafter. RECIST assessments will be performed every 8 weeks (± 1 week) after first doses of IPs until disease progression. Patients will continue the study treatments until:

- objective radiological disease progression, as defined by RECIST 1.1 guidelines,
- unacceptable toxicity or
- discontinuation of IPs for other reasons (patient withdrawal of consent, physician discretion; see Section 3.9, Section 3.10 and Section 3.11).
- Severe non-compliance with the protocol.

4.3 Follow-up period

If both study treatments are discontinued, patients should undergo the assessments required at the discontinuation visit (see Table 5), whether or not radiological disease progression has occurred. A safety follow-up visit should be conducted 30 days after the discontinuation visit. Any serious and/or non-serious AEs ongoing at this time should be followed-up to resolution or until, in the Investigator's opinion, the condition is unlikely to improve or resolve due to

the patient's underlying disease. Descriptions of the procedures for the follow-up visit are included in the Schedule of Assessment (Table 5).

Assessments in the post study treatments follow-up period (following discontinuation of IPs), depend on whether a patient discontinues study treatments in the presence or absence of radiological disease progression.

4.3.1 Discontinuation of study treatments due to disease progression

If a patient discontinues IPs because of radiological disease progression, she will be followed up for survival every 8 weeks (relative to first dose). Survival information may be obtained via telephone contact with the patient, patient's family or by contact with the patient's current physician.

4.3.2 Discontinuation of study treatments in the absence of disease progression

If a patient discontinues IPs in the absence of radiological disease progression, RECIST assessments for disease progression should continue to be performed every 8 weeks (± 1 week) until radiological disease progression or withdrawal of consent. Once a patient has radiological disease progression, she will be followed up as described in Section 4.3.1 above.

Once patients have been discontinued from the IPs, other treatment options will be at the discretion of the Investigator. All subsequent anti-cancer treatments should be recorded according to Section 7.8. If the patient is lost to follow-up, then this should be noted in the eCRF.

4.4 Final protocol visit

Patients who continue to receive clinical benefit without meeting any discontinuation criteria during the study, will complete a FPV which will occur at their last scheduled visit prior to data cut-off for the primary analysis. Beyond the FPV, patients may continue to receive cediranib and/or olaparib if they are deriving clinical benefit in the opinion of the investigator, and not fulfilling any discontinuation criteria.

Beyond the FPV, patients continuing to receive IPs are to be treated as described in Section 4.5.

4.5 End of study

The end of the study is defined as 'the last visit of the last patient undergoing the study' (ie, last subject last visit [LSLV]) or when the Sponsor decides to discontinue the study.

There will be a primary data cut-off defined at approximately 8 months (LSLV) after the last patient received her first dose of study treatment. This primary data cut-off will be followed by clinical database lock when all data for all patients have been collected. The primary data analysis will be performed and a Clinical Study Report (CSR) written based on this data set.

Patients who continue to receive clinical benefit without meeting any discontinuation criteria during the study, will complete a FPV which will occur at their last scheduled visit prior to primary data cut-off. Beyond the FPV, patients may continue to receive cediranib and/or olaparib (to be provided by the Sponsor), if they are deriving clinical benefit in the opinion of the investigator, and not fulfilling any discontinuation criteria.

Such patients are to be followed in accordance with the Medical Standard of Care and as deemed appropriate by the Investigators. Serious adverse event reporting (on paper) will continue to ensure safety data collection and monitoring of the patients while receiving the investigational product. It is recommended that investigators continue to observe ongoing patients at the frequency employed prior to the FPV. Protocol dose modification and stopping criteria are to be followed while a patient is receiving cediranib and/or olaparib. Restrictions regarding concomitant medications (Section 7.7) must be followed while the patient is receiving cediranib and/or olaparib. A change in the dose/schedule of cediranib and/or olaparib should only occur for safety reasons, based on the Investigator's judgement, and should generally follow the approach for dose reduction and discontinuation as described in this protocol. Combining cediranib and/or olaparib with other anti-cancer therapy is not allowed.

If in the opinion of the investigator, a patient is no longer receiving clinical benefit from the IPs beyond the FPV, then the IPs will be stopped. The Investigator will inform AstraZeneca when a patient discontinues the IPs. Patients must return unused medication during routine clinic visits; drug accountability information must continue to be collected in patient source documents until the patient discontinues treatment. Patients will continue to be monitored for all SAEs and pregnancies while receiving IPs and for 30 days after the last dose of IPs.

5. STUDY ASSESSMENTS

The RAVE Web Based Data Capture (WBDC) system will be used for data collection. The investigator will ensure that data are recorded on the eCRFs as specified in the study protocol and in accordance with the eCRF completion guidelines.

The investigator ensures the accuracy, completeness, and timeliness of the data recorded in the eCRF and the provision of answers to data queries according to the Clinical Study Agreement (CSA). The Investigator will sign the completed eCRFs. A copy of the completed eCRFs will be archived at the study site.

5.1 Efficacy assessments

5.1.1 Tumor assessments by CT or MRI scans

Radiological assessment should use the same modality of imaging throughout the trial. Contrast-enhanced CT scan is preferred but MRI is acceptable where CT is contraindicated. Please refer to the Image Acquisition Guidelines and Site Operations Manual for a quick reference guide for image acquisition and data handling.

Baseline tumor assessment should include CT/MRI of the chest, abdomen and pelvis within 28 days prior to the start of IPs. Follow-up CT/ MRI tumor assessments will cover chest (in those patients with disease in the chest or upper abdomen lymphadenopathy at baseline), abdomen and pelvis with any other regions imaged at baseline where disease was present. Any other sites at which new disease is suspected should also be appropriately imaged. Radiological examinations performed in the conduct of this study should be retained at site as source data. Copies of all imaging assessments including unscheduled visit scans will be collected on an ongoing basis and sent to Contract Research Organization (CRO) for ICR (see Section 5.1.3).

All treatment decisions will be based on Investigator assessment of scans. All patients will have RECIST 1.1 tumor assessments at screening (within 28 days prior to the date of first dose of IPs) and thereafter every 8 weeks (± 1 week) relative to the date of first dose of IPs (Table 5) until objective radiological disease progression as defined by RECIST 1.1 and as determined by the Investigator, or unless they withdraw consent. Objective radiological response on treatment (CR or PR) will need to be confirmed during next RECIST 1.1 visit assessment.

If a patient discontinues IPs for any reason other than disease progression or withdrawal of consent, RECIST 1.1 assessments should continue as per protocol schedule until evidence of objective radiological progression or withdrawal of consent (see Section 4.3).

It is important to follow the assessment schedule as closely as possible. If scans are performed outside of scheduled visit (± 1 week window) and the patient has not progressed, every attempt should be made to perform the subsequent scans at their scheduled time points.

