5.1.3 Central reading of scans

An independent review of all scans used in the assessment of tumors using RECIST 1.1 will be conducted. Copies of all imaging assessments including unscheduled visit scans will be collected on an ongoing basis and sent to an AstraZeneca appointed CRO for central analysis. If a patient had tumor biopsy during screening, but after the baseline RECIST scan, information on which lesion was biopsied will be provided to ICR so that such lesion is not chosen as the target lesion. Results of this independent review will not be communicated to Investigators, and the management of patients will be based solely upon the results of the RECIST assessment conducted by the Investigator. The primary analysis of ORR will be based on ICR assessment.

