8.4.2 Secondary endpoints

Duration of response (DoR)

DoR will be defined as the time from the date of first documented response, (that is subsequently confirmed) until date of documented progression or death in the absence of disease progression. The date of the response start will be defined as the latest of the dates contributing towards the first visit response of PR or CR. If the response is not confirmed, it will not be included. The end of response should coincide with the date of progression or death from any cause used for the PFS endpoint. If a patient does not progress following a response, then their duration of response will use the PFS censoring time.

Disease control rate (DCR)

DCR is defined as the percentage of patients who have a best overall response of CR or PR or SD (at 6 months).

Progression free survival (PFS)

PFS is defined as the time from date of first dose until the date of objective disease progression or death (by any cause in the absence of progression) regardless of whether the patient withdraws from study therapy or receives another anti-cancer therapy prior to progression. Patients who have not progressed or died at the time of analysis will be censored at the time of the latest date of assessment from their last evaluable RECIST assessment. However, if the patient progresses or dies after three or more missed RECIST assessments visits, the patient will be censored at the time of the latest evaluable RECIST assessment. If the patient has no evaluable visits or does not have baseline data they will be censored at 0 days unless they die within two visits of baseline.

The PFS time will always be derived based on scan/assessment dates not visit dates. RECIST assessments/scans contributing towards a particular visit may be performed on different dates. The following rules will be applied:

- Date of progression will be determined based on the earliest of the dates of the component that triggered the progression
- When censoring a patient for PFS the patient will be censored at the latest of the dates contributing to a particular overall visit assessment.

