In the D8488C00001 study, 18-Fluoro-deoxyglucose positron emission tomography (FDG-PET) scans may be used as a method for identifying new lesions, according with the following algorithm: New lesions will be recorded where there is positive 18-Fluoro-deoxyglucose uptake³ not present on baseline FDG-PET scan or in a location corresponding to a new lesion on CT/MRI at the same follow-up visit. If there is no baseline FDG-PET scan available, and no evidence of new lesions on CT/MRI scans then follow-up CT/MRI assessments should be continued, scheduled as per protocol or clinical indicated, in order to confirm new lesions.

TUMOUR RESPONSE EVALUATION

Schedule of evaluation

³ A positive FDG-PET scan lesion should be reported only when an uptake greater than twice that of the surrounding tissue is observed.

Baseline assessments should encompass all areas of known predilection for metastases in the disease under evaluation and should additionally investigate areas that may be involved based on signs and symptoms of individual patients and should be performed within the 28 days prior to randomisation and ideally as close as possible before the start of study treatment (see the Schedule of Assessments [Table 5] in the main body of the protocol). Follow-up assessments will be performed every 8 weeks (± 1 week), relative to first dose of investigational product(s) until confirmed objective disease progression as defined by RECIST 1.1 (irrespective of the reason for stopping treatment and/or subsequent therapy).

Any other sites at which new disease is suspected should also be adequately imaged at follow-up.

If an unscheduled assessment was performed and the patient has not progressed, every attempt should be made to perform the subsequent assessments at their scheduled visits. This schedule is to be followed in order to minimise any unintentional bias caused by some patients being assessed at a different frequency than other patients.

Target lesions

Documentation of target lesions

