3. PRIMARY AND SECONDARY VARIABLES

The primary analysis of ORR (primary endpoint), DoR, PFS, and DCR (secondary endpoints) will be reported based on the Independent Central Review of radiological data. ORR will also be reported based on the Investigator assessment (secondary endpoint).

In addition, sensitivity analyses will be performed of DoR, PFS, and DCR using investigators assessments of RECIST.

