3.2.2 Secondary endpoints

Duration of response (DoR)

DoR will be defined as the time from the date of first documented response (which is subsequently confirmed) until date of documented progression or death in the absence of disease progression (ie, date of PFS event or censoring – date of first response + 1). The end of response should coincide with the date of progression or death from any cause used for the PFS endpoint. The time of the initial response will be defined as the latest of the dates contributing towards the first visit that was CR or PR that was subsequently confirmed.

If a patient does not progress following a response, then their DoR will use the PFS censoring time.

Disease control rate

Disease control rate is defined as the percentage of patients who have a best overall response of CR or PR or SD (at 6 months). For SD to be counted, patients should have demonstrated SD for a minimum interval of 23 weeks (24 weeks minus 1 week to allow for an early assessment within the assessment window, ie, 161 days) following the start of treatment.

Progression free survival (PFS)

PFS is defined as the time from date of first dose until the date of objective disease progression or death (by any cause in the absence of progression) regardless of whether the patient withdraws from study therapy or receives another anti-cancer therapy prior to progression (i.e. date of PFS event or censoring – date of first dose + 1). Patients who have not progressed or died at the time of analysis will be censored at the time of the latest date of assessment from their last evaluable RECIST assessment. However, if the patient progresses or dies after two or more missed RECIST assessments visits, the patient will be censored at the time of the latest evaluable RECIST assessment prior to the two missed visits.

If the patient has no evaluable visits or does not have baseline data they will be censored at Day 1 unless they die within 2 visits of baseline (16 weeks plus 1 week allowing for a late assessment within the visit window).

The PFS time will always be derived based on scan/assessment dates not visit dates. RECIST assessments/scans contributing towards a particular visit may be performed on different dates. The following rules will be applied:

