4.2.7.3 Sensitivity analysis

ORR, DCR, DoR and PFS will be re-analyzed at the time of the primary analysis using the investigator assessment of tumor response instead of ICR assessment, as sensitivity analyses.

ORR and exact 95% CI (Clopper Pearson) will be presented for the following:

- ORR by investigator assessment. The numerator (number of confirmed responses) will be based on RECIST as per investigator assessment and the denominator will be based on the full analysis set

- ORR for both confirmed and unconfirmed responses based on ICR assessment. The numerator will include unconfirmed responses in addition to confirmed responses and the denominator will be based on the EFR set.

Sensitivity analyses of PFS, DoR and DCR using the investigators assessment of RECIST will be performed in an analogous manner to those using the ICR described in Section 4.2.7.2 above.

In addition, ORR and BOR using the ICR will be summarised for the FAS.

For patients where measurable disease at baseline is not confirmed by the ICR and who therefore appear in the sensitivity analysis using FAS, but not the primary analysis set (evaluable for response), a detailed description of the reasons for being considered not evaluable will be described in the CSR.

A further comparison of each type of overall objective response (CR, PR, SD, PD, NE or without measurable disease at baseline) between investigator and ICR will be presented using the full analysis set. Details for the patients identified as responders by ICR and not by the investigator, as well as by the investigator and not by ICR will be given.

The concordance between response as assessed by ICR and by investigator with the full analysis set will be summarised by cross-tabulation of the number and percentage of patients with:

- Response declared by investigator and ICR
- Response declared by investigator but not ICR
- Response declared by ICR but not investigator
- No response declared by both investigator and ICR

The overall concordance rate will be calculated as the total number of agreements between investigator and ICR divided by the total sample size.

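### Scheduled scans stop at investigator-declared progression, so ICR PFS and DoR are informatively censored when ICR has not yet called progression, and no planned analysis bounds the resulting upward bias

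*Protocol*

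**What the plan says.** - **When scans stop.** Protocol 5.1.1 sets scans every 8 weeks "until objective radiological disease progression as defined by RECIST 1.1 and as determined by the Investigator", or until consent is withdrawn. Protocol 4.3.2 continues them after treatment stops only for patients without radiological progression.
- **No feedback.** Protocol 5.1.3: "Results of this independent review will not be communicated to Investigators". ICR disagreement therefore cannot keep a patient on the scan schedule.
- **Which assessor is main.** SAP 3: "The primary analysis of ORR (primary endpoint), DoR, PFS, and DCR (secondary endpoints) will be reported based on the Independent Central Review".
- **Censoring.** SAP 3.2.2: "Patients who have not progressed or died at the time of analysis will be censored at the time of the latest date of assessment" of the last evaluable RECIST visit. DoR takes over the PFS censoring time.
- **Late events.** SAP 3.2.2: "if the patient progresses or dies after two or more missed RECIST assessments visits, the patient will be censored". Protocol 8.4.2 sets a different limit: "if the patient progresses or dies after three or more missed RECIST assessments visits". Deaths before the limit remain events.
- **Planned checks.** SAP 4.2.7.3 repeats ORR, DCR, DoR and PFS "using the investigator assessment of tumor response instead of ICR assessment, as sensitivity analyses". Its ICR-versus-investigator comparison and concordance tables concern objective response. None tabulates progression status or date by assessor.
- **Appendix F.** The schedule-of-evaluation text runs scans "until confirmed objective disease progression as defined by RECIST 1.1", while the same appendix, under confirmation of progression, leaves confirmation to the investigator and does not require it.

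**The concern.** Kaplan-Meier estimation assumes that a patient censored at a given time has the same outlook as those still being followed. Here, the patients censored at the investigator's progression scan are those whose treating physician has just seen progression. Many would have been called progressed by ICR at the next scan, had there been one. Treating them as average survivors raises the ICR PFS curve. It also raises ICR DoR, which uses the same censoring date.

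The trial has one arm, so there is no control in which the bias could cancel. The durability estimates will be read against outside values; Protocol 1.1.1 and 1.3 cite a median PFS of 3 to 4 months in platinum-resistant disease.

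**Working it through.** **1. The plan's own figures.** Protocol 8.2 expects 80% PFS events and 57% OS events, with medians of 6 and 12 months and a cut-off 8 months after the last first dose. The revised recruitment time is not stated. With uniform accrual over R months and minimum follow-up F, the expected event share is 1 − [exp(−λF) − exp(−λ(F+R))]/(λR), where λ = ln 2/median. Take F = 8 and assume R = 14:
- PFS: 1 − (0.397 − 0.079)/1.617 = 80.3%.
- OS: 1 − (0.630 − 0.281)/0.809 = 56.8%.

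Both agree with the plan, so this accrual pattern is used below. 80% of 60 patients is 48 events.

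**2. One patient.** The investigator calls progression at week 16 and ICR reads that scan as stable. Scheduled imaging ends and the site does not learn the ICR reading. If she is alive at cut-off with no further scan, she is censored at week 16 for ICR PFS. If she was an ICR responder, her ICR DoR is censored on the same date.

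**3. Size for PFS.** Inputs from the documents: median PFS 6 months, 8-weekly scans, 8 months' minimum follow-up. Assumptions:
- ICR lags in a share q of investigator progressions, and then calls progression one scan later.
- Median survival after progression is 6 months.
- Deaths within 2 × 8 + 1 = 17 weeks of the last scan count as events (the SAP limit plus the visit window).

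Simulated 6-month PFS:

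| q | As planned | If scans continued | Bias (points) | Investigator PD counted as event |
|---|---|---|---|---|
| 10% | 55.3% | 53.7% | 1.6 | 52.7% |
| 20% | 58.2% | 54.9% | 3.3 | 52.7% |
| 30% | 61.1% | 56.0% | 5.1 | 52.8% |

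A separately coded run of the same model gives biases of 1.8 (56.0 − 54.2), 3.7 (59.1 − 55.4) and 5.7 (62.2 − 56.5). At q = 20%, about 9% of patients are censored this way, or 0.09 × 60 = 5 to 6 patients.

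Medians taken on the 8-week grid move in whole-scan steps, so they are a poor guide. A continuous-time version gives these medians (scans continued / as planned / investigator):
- q = 10%: 6.2 / 6.5 / 6.0 months.
- q = 20%: 6.4 / 7.0 / 6.0 months.
- q = 30%: 6.5 / 7.6 / 6.0 months.

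Observed ICR events fall from 48 to about 45, 42 and 39 of 60. The Protocol's three-visit limit also gives 7.0 months at q = 20%.

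**4. Does investigator-assessed PFS already bound the bias?** In the table it does, because ICR is never earlier than the investigator; the last column is then both investigator PFS and the proposed composite. Now let ICR be one scan earlier in 15% of patients and one scan later in 10%:

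| Analysis | 6-month PFS |
|---|---|
| ICR as planned | 53.9% |
| ICR if scans continued | 52.3% |
| Investigator | 52.8% |
| ICR, with investigator PD counted where ICR has none | 51.3% |

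The two planned results span 52.8% to 53.9% and miss the target of 52.3%. The composite and the planned ICR result span 51.3% to 53.9% and contain it.

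**5. What the composite does not do.** At q = 20%, planned minus composite is 58.2 − 52.7 = 5.5 points, against a bias of 3.3. It overcorrects, because it dates the event at the investigator's scan when ICR would have called it later.

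No size was computed for DoR. The direction is the same because the censoring date is shared.

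**The case against.** Several points on the other side stand.

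- **There is already a check.** Investigator-assessed PFS is free of this censoring and uses the same analysis set (FAS, SAP Table 2). If ICR is never earlier than the investigator, the composite adds nothing to it for PFS. Its gain comes when ICR is sometimes earlier, and for DoR, where the planned swap also changes the responders and moves from EFR to FAS.
- **The composite bounds the bias and does not isolate it.** The 5.5 against 3.3 points above shows this.
- **Not every disagreement leads to censoring.** Deaths before the missed-visit limit count. All scans, including unscheduled ones, go to ICR (Protocol 5.1.3), and unscheduled assessments enter PFS (SAP 3.2.2). Nothing of this kind arises when ICR calls progression first.
- **The response tables show some disagreement.** SAP 4.2.7.3 compares best response by category, including PD, but not progression dates.
- **The stakes are modest.** No test, threshold or futility rule uses PFS or DoR. At q = 20% the bias is below one standard error of 6-month PFS with 60 patients: √(0.55 × 0.45/60) = 6.4 points, ignoring censoring. It is systematic, however, and the confidence interval does not reflect it.

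A reader might also infer that the Appendix F wording worsens the bias. The text does not support that. Scanning until confirmed progression would mean more imaging after the investigator's call and so less of this censoring. What remains is an inconsistency between Appendix F and Protocol 5.1.1.

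**Conclusion.** The concern holds in a limited form. Ending scheduled scans at investigator progression, without ICR feedback, informatively censors ICR PFS and DoR in patients where ICR lags, and biases both upward. At an assumed 10% to 30% lag, 6-month ICR PFS is about 2 to 5-6 points too high. This rests on the assumed lag rate, a one-scan delay, 6 months' median survival after progression and 14 months' accrual. The only ICR-versus-investigator figure in the documents is the 1.5% lower response rate in Protocol 8.2, which says nothing about progression.

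Two stronger readings are not supported. One is that the plan has no protection at all: investigator-assessed PFS and DoR are planned, though they need not bound the bias. The other is that the trial's decision is compromised: PFS and DoR are secondary and descriptive, and the primary endpoint is ICR ORR. This is a cheap improvement to reporting.

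**What to change.** Keep the scan schedule. In SAP 4.2.7.3:

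1. Add a sensitivity analysis of ICR PFS (FAS) and ICR DoR (ICR responders in the EFR set) in which a patient with investigator progression and no ICR progression has an event at the investigator's progression date.
2. Report the number and percentage of patients so affected, with a cross-tabulation of progression status and date by assessor.
3. State that the result is a conservative lower bound. With the planned ICR estimate it brackets the value that continued scanning would have given, provided the censored patients are at higher risk than those still followed. It does not isolate the bias.

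Separately, reconcile the Appendix F scan-schedule sentence with Protocol 5.1.1 and with the appendix's own text on confirmation of progression, and reconcile the two-visit and three-visit limits in SAP 3.2.2 and Protocol 8.4.2.

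The cost is SAP wording and a few outputs from data already held, with no extra scans or reads. The downside is a less favorable PFS and DoR shown beside the main ones.
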